5.3 Feasibility

The feasibility of answering the primary research question will be addressed after the first 100 patients have been randomized and delivered. These data would be presented to the Data and Safety Monitoring Committee (DSMC) before any comparison by group. The DSMC would be charged with making a recommendation regarding potential revision of the sample size.

5.4 Interim Analysis

The DSMC meets in person at least once per year and more often if recommended by the committee. Before each of the annual meetings, a formal detailed report will be written by the Biostatistical Coordinating Center (BCC) which presents all baseline variables, protocol adherence, side effects, all adverse events reported, as well as center performance in terms of recruitment, data quality, loss to follow-up and protocol violations.

Once sufficient patients have been accrued into the trial, the report will also include a formal interim analysis evaluating the primary outcome by treatment group. For this evaluation, a cohort of patients is chosen consisting of all patients randomized before a certain date so that the analysis cohort does not depend on gestational age at delivery.

The main statistical issue relevant to interim analysis is the problem of performing multiple tests of significance on accumulating data. For this trial, the group sequential method of Lan and DeMets will be used to characterize the rate at which the type I error is spent.³⁶ This method is flexible with regard to the timing of the interim analyses. Asymmetric stopping boundaries will be used for the Lan-DeMets procedure. The upper boundary which describes the stopping rule for benefit will be based on 1-sided type I error of .0125 and the Lan-DeMets generalization of the O'Brien-Fleming boundary. The lower boundary will be based on a less stringent stopping rule: 1-sided type I error of .05 and the Lan-DeMets generalization of the Pocock type boundary. If recruitment proceeds as planned and annual analyses are conducted, it is expected that two interim analyses will be conducted at approximately 35% and 65% of the final sample size of 630.

If a maternal death occurs after randomization and before discharge following delivery recruitment to the trial will be paused until the DSMC has been convened to determine whether the study should proceed.

It is often useful to calculate conditional power given the observed data to date, and conditional on the future data showing the originally assumed design effect. If this conditional power is low (under 10 percent) the DSMC may consider termination for futility if the accrual rate is slow with confidence that the Type II error is not greatly inflated.³⁷

It is recognized that any decision to terminate the study would not be reached solely on statistical grounds but on a number of complex clinical and statistical considerations.

5.5 Analysis Plan

All statistical analyses will be based upon the total cohort of patients randomized into the trial. Although data on some patients may be missing, all relevant data available from each patient will be employed in the analyses. Patients will be included in the treatment group to which they were randomly assigned regardless of compliance.

The primary analysis will consist of a simple comparison of binomial proportions. The relative risks and confidence intervals will be reported. The individual components of the composite outcome will also be examined. If the treatment groups are found to differ on a pre-treatment factor known to be a risk factor for the outcome, the statistical analysis will adjust for these differences. An evaluation of treatment by center interaction will be included. An analysis adjusting by center also will be performed to ensure that center differences do not change the conclusion.

If the two groups show a difference in the incidence of the primary outcome, interactions will be evaluated and subgroup analyses conducted to determine whether the effect prevails throughout particular subgroups of patients. Indeed, NIH guidelines require investigators to evaluate consistency between the genders and across racial subgroups (see Section 5.5.1). It should be noted, however, that subgroup analyses have been greatly abused, particularly when there is no overall treatment difference.³⁸ There is a strong temptation to search for a specific subpopulation in which the therapy is nevertheless effective. Yusuf et al. concluded “*the overall ‘average’ result of a randomized clinical trial is usually a more reliable estimate of the treatment effect in the various subgroups examined than are the observed effects in individual subgroups.*”³⁹ Thus subgroup analyses will be interpreted with care.

It is generally acknowledged that subgroup analysis that is pre-specified in the protocol has more validity than ad-hoc comparisons. The following factors will be considered for subgroup analysis, if there is a significant interaction between the factor of interest and the treatment effect.

- Race/ethnicity (see below)
- Gestational age at randomization (< 20 weeks and ≥ 20 weeks)
- Cervical length at randomization (< 15 and ≥ 15 mm; < 20 mm and ≥ 20 mm)
- Screening to randomization interval
- Debris/funneling on randomization ultrasound
- Chorionicity
- Obesity by BMI category
- Parity
- Bacterial vaginosis/Nugent score at enrollment—Nugent ≥ 7 with pH > 4.4
- Fetal fibronectin positive
- Type of conception/use of ART
- Prior cervical surgery including LOOP/ LEEP

Loss to follow-up will be defined as no information regarding pregnancy prior to 35 weeks. Those defined as lost to follow-up will not be included in the primary analysis. It is expected that the loss to follow-up rate will be very low. For trials conducted by the MFMU Network, the loss to follow-up rate has typically been under 2 percent. However, a sensitivity analysis will be performed including patients lost to follow-up with different assumptions regarding their outcome, to determine whether the results are robust.

Since many of the secondary endpoints are dichotomous variables like the primary outcome, standard statistical methods for rates and proportions will be appropriate. The Wilcoxon rank sum test will be used to compare continuous variables, and survival analysis methodology will be used to compare time-to-event variables, such as time to delivery or fetal demise and gestational age at delivery or fetal demise.

In general, analyses of data will be conducted to address the primary and secondary research questions of the trial, and other interrelationships among elements of study data of interest to the investigators and of relevance to the objectives of the study.

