2.2 Cervical Length and the Risk of Preterm Birth

A short cervix during pregnancy, as measured by endovaginal ultrasound, was first reported to be a significant risk factor for preterm delivery by Andersen et al. in 1990.¹⁴ This study found that in an unselected population of 113 gravidas, a cervix of less than 39 mm before 30 weeks gestation was a significant risk factor for early delivery. Moreover, the authors found the risk of preterm delivery to be inversely proportional to cervical length and that the risk increased significantly with shorter cervical measurements.

Subsequently, multiple studies have confirmed this finding in both singleton and twin pregnancies, including the Preterm Prediction Study conducted by the MFMU Network from 1992-1995. The Prediction Study was a prospective observational cohort study evaluating associations between various markers and subsequent spontaneous preterm delivery. A total of 2915 women with a singleton gestation and 151 with a twin gestation had a cervical length measurement at 22-24 weeks of gestation by trained and certified sonographers. In the singleton cohort, the mean cervical length was 35 mm with a standard deviation of 8 mm and in the twin cohort the mean was 33 mm with a standard deviation of 10 mm. In the singleton cohort, women with cervical length at or below a particular percentile were compared with those who had cervical length values above the 75th percentile. The relative risk for spontaneous preterm delivery at less than 35 weeks was 3.8 with a 95% confidence interval (CI) of 2.3 – 6.2 at or below the 25th percentile, 6.2 (95% CI: 3.8 – 10) at or below the 10th percentile and 9.5 (95% CI: 6.0 – 15.2) at or below the 5th percentile.¹⁵ A cervical length of 25 mm was approximately the 9th percentile for singletons and has become the adopted cutoff for the diagnosis of short cervical length in singleton gestations.

In the twin cohort, as in singletons, women with a short cervix were at increased risk for preterm birth (53.9% versus 26.5% in the group with cervical length >25 mm, $p=0.01$). After adjusting for other factors, a short cervix was associated with a nearly 8-fold increase in the odds of a spontaneous preterm birth <32 weeks.¹⁶ Similarly, a meta-analysis demonstrated that asymptomatic women with twin gestations and cervical length ≤ 20 mm at 20-24 weeks had a nearly 10-fold increase in the risk of preterm birth prior to 34 weeks.¹⁷

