3.4.3 Cervical Length Determination

The length of the cervix will be measured according to the transvaginal ultrasound method described by Iams et al.¹⁵ With a real-time ultrasound probe placed in the anterior fornix of the vagina while the woman's bladder is empty, the appropriate sagittal view will be obtained by the location of the triangular area of echodensity at the external os, a V-shaped notch at the internal os, and a faint line of echodensity or echolucency between the two. After the initial image is obtained once the probe is in place, the probe will be withdrawn until the image blurs, and then the probe will be reapplied with only enough pressure to restore the image. The cervix will be measured three times along the line made by the interface of the mucosal surfaces, with calipers placed at the external and internal os. Dynamic change in cervical length will be considered by observing for spontaneous dynamic change or by applying mild fundal pressure for 15-30 seconds and then re-measuring the cervical length. The final cervical measurement reported will be the shortest best measure that clearly meets the above criteria – an averaging approach will not be used.

All cervical length measurements employed for screening and enrollment will be performed by a sonographer who has been trained and certified in the appropriate technique. Documentation of education and proficiency in appropriate technique and competency in cervical assessment will be required. Required documentation includes a Fetal Medicine Foundation Certificate of Competence in cervical assessment, or certification through the Perinatal Quality Foundation's Cervical Length Education and Review (CLEAR) program, or sonographer participation in a previous NICHD study.

An advisory committee of ultrasound experts will be assembled to review a random sampling of approximately 10-15% of enrollment vaginal ultrasound cervical length measurements as validation of appropriate imaging techniques.

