Each center will develop its own consent forms according to the requirements of its own institutional review board using the model screening and study consent forms in Appendix B. Each center will also develop its own patient research authorization documents, as required by the HIPAA Privacy Rule, following the guidelines of its own institution. A copy of the signed screening consent form and, if applicable, the consent form for the study will be provided to the patient.

Women who are not fluent in English will be enrolled by a person fluent in their language, if possible. Both verbal and written informed consent and authorization will be obtained in that language; if this is not possible the patient will be excluded.

3.6 *Randomization Method and Masking*

Consenting women will initially be assigned to progesterone, pessary or placebo in a 1:1:1 ratio according to a randomization sequence prepared and maintained centrally by the Biostatistical Coordinating Center (BCC). The two study medication arms of the study (progesterone or placebo) are double masked; neither the patient nor the clinical staff will be aware of the treatment assignment.

The simple urn method will be used to generate the randomization sequences because it provides a high probability of balance in treatment assignments, it is unpredictable, and it allows an explicit randomization analysis to be conducted with relative ease.^{34,35} Randomization will be stratified by clinical site to assure balance between the two treatment groups with respect to anticipated differences in the clinic populations and possible differences in patient management.

4 Study Procedures

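### The primary comparison leaves out site and baseline cervical length, and covariate adjustment waits on an undefined imbalance: a valid test that forgoes an inexpensive, probably modest gain in precision

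*Combined protocol and SAP*

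**What the plan says.** The primary analysis is given in one sentence of section 5.5: "The primary analysis will consist of a simple comparison of binomial proportions". Relative risks with confidence intervals are to be reported. Section 3.6 sets the design: "Randomization will be stratified by clinical site to assure balance between the two treatment groups".

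The same paragraph of 5.5 provides for adjustment in two ways. For site: "An analysis adjusting by center also will be performed to ensure that center differences do not change the conclusion", together with a look at treatment-by-center interaction. For other baseline factors, adjustment is conditional: "If the treatment groups are found to differ on a pre-treatment factor known to be a risk factor for the outcome", the analysis will take the difference into account. The paragraph does not list those factors, define when arms differ, name a model, or say whether the adjusted result would replace the simple one.

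Cervical length is known for every randomized woman, because a transvaginal length below 30 mm is an entry criterion with no lower limit (3.4.1), measured to a common standard (3.4.3): "All cervical length measurements employed for screening and enrollment will be performed by a sonographer who has been trained and certified". In the analysis of treatment effect it is listed only as a subgroup factor: "Cervical length at randomization (< 15 and ≥ 15 mm; < 20 mm and ≥ 20 mm".

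**The concern.** When randomization is stratified, the primary analysis would normally use the strata, and a prognostic baseline value that is already collected would normally be a pre-specified covariate. Leaving both out gives a standard error at least as large as it needs to be in a large sample. The trial has most to gain at the smaller effect, for which section 5.2 claims only at least 80% power.

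The conditional clause is the less comfortable part. As written, whether the headline analysis is adjusted, and for what, could be settled after the arms have been compared at baseline. The answer could also differ between the interim looks in 5.4 and the final analysis.

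**Working it through.** **Inputs.** From 5.2 and Appendix A: placebo rate 55%; one-third reduction (36.7%) or 30% reduction (38.5%); two-sided alpha 2.5% per comparison (z = 2.241); 630 women, 210 per arm; 5% crossover. The documents give no R² or odds ratio for cervical length among twin pregnancies below 30 mm and no between-site variance. Both are assumed below, over a range. Power is fixed-sample and ignores the interim looks and loss to follow-up.

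**1. The plan's own figure.** n per arm = [2.241·√(2p̄(1−p̄)) + 1.282·√(p0(1−p0)+p1(1−p1))]² / (p0−p1)². For 55% against 36.67% this is 181.1, so 182, and 190 after rounding up to the next 10. All 18 cells of Table 3 reproduce this way. The crossover factor is 1/0.95² = 1.108, and 190 × 1.108 = 210.5 per arm, or 631.6 in all, against the stated 630.

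**2. Power of the simple test.** The 1.108 factor corresponds to 5% of the active arm having the placebo rate.
- One-third: active rate 0.95×0.3667 + 0.05×0.55 = 0.3758. Then (0.1742·√210 − 1.5805)/0.6943 = (2.5239 − 1.5805)/0.6943 = 1.359, which gives 91.3%.
- 30%: active rate 0.95×0.385 + 0.05×0.55 = 0.3933, which gives 83.9%.

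Both meet the stated 90% and 80%. If 5% crossed over in both arms (0.5408 against 0.3758, and 0.5418 against 0.3933), power would be 87.9% and 79.3%, but that is not what the plan's factor describes.

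**3. Gain from adjustment.** Adjustment multiplies the variance by (1−R²), so the effective size per arm is 210/(1−R²), the gain in women is 630·R², and the interval width shrinks by √(1−R²).

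| Assumed R² | Women | Power, one-third | Power, 30% | Interval narrower by |
|---|---|---|---|---|
| 0 | 0 | 91.3% | 83.9% | 0 |
| 0.02 | 13 | 91.9% | 84.7% | 1% |
| 0.05 | 32 | 92.7% | 85.8% | 2.5% |
| 0.10 | 63 | 94.0% | 87.8% | 5% |

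**4. Which R² is plausible.** Two rough guides come from section 2.2, and neither describes this population.
- Twins of any cervical length: preterm birth "53.9% versus 26.5% in the group with cervical length >25 mm". Table 1 puts 21 mm at the 10th and 28 mm at the 25th percentile, so assume 18% are short. The mean rate is 0.18×0.539 + 0.82×0.265 = 0.314, and R² = 0.18×0.82×0.274²/(0.314×0.686) ≈ 0.05.
- Singletons: relative risks 3.8, 6.2 and 9.5 at or below the 25th, 10th and 5th percentiles (30, 26 and 22 mm). Separated into bands these are (25×3.8 − 10×6.2)/15 = 2.2, (10×6.2 − 5×9.5)/5 = 2.9, and 9.5. Suppose they carry over as odds ratios to a 55% rate with band weights 15:5:5. The band rates are then 47.2%, 54.1% and 79.4%, and R² = [0.6×0.078² + 0.2×0.009² + 0.2×0.244²]/(0.55×0.45) ≈ 0.06. With half the log-odds gradient it is about 0.02.

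**5. Simulation.** Settings: 210 per arm, 18 sites, allocation balanced within site, 2,000 runs per power setting (Monte Carlo error about 0.6 points), and a linear risk-difference model on cervical length plus site with robust standard errors.

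| Odds ratio per SD | Site SD (log-odds) | One-third: simple → adjusted | 30%: simple → adjusted |
|---|---|---|---|
| 1.25 | 0.2 | 91.9 → 91.7% | 83.4 → 83.7% |
| 1.5 | 0.3 | 92.3 → 93.4% | 85.7 → 87.5% |
| 2.0 | 0.3 | 92.0 → 94.7% | 84.7 → 88.1% |

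Under no effect (4,000 runs), rejection was 2.7–2.8% for the simple test and 2.6–2.8% adjusted, against 2.5% nominal and a Monte Carlo error of about 0.25 points. Logistic standardization over cervical length alone gave 91.7%, 92.8% and 94.2% at one-third. The full recommended model, logistic with site, was not simulated. Adjustment for site alone added nothing measurable.

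**The case against.** The strongest reply is that nothing is broken. The trial was sized for the simple test, that test keeps its error rate and reaches its stated power, and a marginal relative risk is transparent. A center-adjusted analysis is already planned. All of this stands.

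The prognostic argument can also be pressed too far. A reader might infer from section 2.2 ("a short cervix was associated with a nearly 8-fold increase in the odds of a spontaneous preterm birth") that cervical length must be a dominant predictor here. That figure is for spontaneous birth before 32 weeks in twins not selected for length. The primary outcome is any delivery or fetal demise before 35 weeks, in women all below 30 mm, and 5.2 supposes that 20% of these preterm births may be indicated. Section 5.1 shows no visible gradient in the few STTARS women near the cut-off (5 of 10 below 30 mm, 10 of 18 below 32 mm). Those numbers are too small to show that the gradient is flat, and the singleton bands suggest that it is not, but strength in this population remains an assumption.

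Sparse sites are a real cost. At 35% of 630 a comparison holds about 147 women (220 × 2/3), or 8 to 10 per site, depending on whether the fourteen centers of 7.1 or the eighteen of Appendix A are counted.

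None of this defends the imbalance clause, which stays undefined whatever the size of the gain.

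**Conclusion.** The concern holds as a precision and pre-specification point. The primary test ignores the stratification factor and a baseline value recorded for everyone, and the only route to covariate adjustment depends on an observed imbalance with no rule behind it.

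The expected benefit is about 0 to 3 points of power at a one-third reduction and about 0 to 4 at 30%, for R² up to about 0.11. It is nil at an odds ratio near 1.25 per SD. These sizes rest on the assumed R², odds ratios and site variances. Essentially all of the measurable gain comes from cervical length.

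A reader might go further and conclude that the primary test is biased or that the trial is underpowered without adjustment. The documents do not support either: on the plan's own crossover factor the simple test has 91.3% and 83.9% power, and its simulated type I error is close to nominal.

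**What to change.** Before unblinding, amend section 5.5 as follows.

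- Make the primary analysis, at the unchanged alpha of 2.5% two-sided per comparison, a standardized risk ratio and risk difference for each active arm against placebo. Adjust for site and for cervical length at randomization as a continuous variable, with robust standard errors.
- State a rule for pooling small sites, and a fallback if the model does not converge.
- Use the same statistic at the interim looks in 5.4.
- Delete the imbalance-triggered adjustment.
- Keep the simple comparison of proportions as a supportive analysis.

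This needs no new data and no more women. The cost is protocol wording, a somewhat more complex analysis, and thin sites at the first interim look, which the pooling rule is there to handle. If cervical length proves weak, the loss of power is trivial: 0.6 points or less in the checks made.

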5.2 Sample Size and Power

A one-third reduction in preterm birth < 35 weeks was selected as being clinically meaningful. It is assumed that pessary and micronized progesterone are more likely to be effective for preventing spontaneous rather than indicated preterm birth. If 20% of the preterm births at this gestation are indicated (lower than that typically expected since these women will all have a short cervix) and if there is a 40% reduction in spontaneous preterm birth and no reduction in indicated preterm birth, then the overall effect size would be slightly less than a one-third reduction in all preterm births.

Table 3 below shows the sample sizes required to detect 30-33% reduction in PTB < 35 weeks if the rate in the placebo group is 50-60%, with type I error 2.5% 2-sided and power of 90%. Type I error was chosen to be 2.5% 2-sided since there will be two primary comparisons (between pessary and placebo and between progesterone and placebo).

Table 3. Sample Sizes per Group for Different Primary Outcome Rates, Power and Effect Sizes²

Reduction in Primary Outcome Rate	% Power	Primary Outcome Rate in Placebo Group		
		50%	55%	60%
30%	80	210	180	150
	85	240	200	170
	90	270	230	190
33.3%	80	170	140	120
	85	190	160	140
	90	220	190	160

²Rounding up to next 10

In STTARS, women were given a test injection of progesterone (17- α hydroxyprogesterone caproate) and asked to return for randomization in three days or more. A total of 2.7% of women did not return or withdrew consent. Since a compliance run-in such as this is not feasible for PROSPECT, it is assumed conservatively that as many as 5% of the women drop out and effectively become crossovers. This would require an adjustment in the sample size of approximately 10.8%. Thus, adjusting for 5% crossover, a sample size of 630 patients is sufficient to detect a one-third reduction in the primary outcome rate of 55% in the placebo group with 90% power for either the pessary or the progesterone arm, and at least 80% power if the effect size is as low as 30%.

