Assumptions:	❖ Outcome event=delivery < 35 ⁰ weeks gestation or fetal loss ❖ Placebo group event rate =55% ❖ Progesterone group event rate =36.7% (33% reduction) ❖ Pessary group event rate=36.7% (33% reduction) ❖ Type I error = 2.5% (two sided with two primary comparisons) ❖ Power =90% ❖ Adjustment for 5% crossover	Secondary:	❖ Randomization to delivery interval ❖ Gestational age at delivery ❖ Neonatal morbidity and mortality ❖ Lower genital tract or urinary tract infection ❖ Physician interventions including bedrest, cerclage, labor inhibition therapy
Interim Analysis:	❖ Lan-DeMets group sequential method	TIMETABLE	
		Enrollment	❖ April 2015 to September 2018
		Data Collection	❖ April 2015 to June 2019
		Closeout/Analysis	❖ June 2019 to May 2020

References

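### Section 5.5 triggers covariate adjustment by observed imbalance and does not say whether the adjusted or the unadjusted result is confirmatory; one model should be fixed in advance

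*Combined protocol and SAP*

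**What the plan says.** Section 5.5 (Analysis Plan) opens the efficacy analysis with "The primary analysis will consist of a simple comparison of binomial proportions", reported as relative risks with confidence intervals. Later in the same paragraph it adds a condition: "If the treatment groups are found to differ on a pre-treatment factor known to be a risk factor for the outcome", then "the statistical analysis will adjust for these differences". It gives no list of factors, no test or threshold for a difference, no model, no method for an adjusted relative risk, and no rule for a disagreement between the two results.

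The only adjustment planned regardless of balance is for center, as a check: "An analysis adjusting by center also will be performed to ensure that center differences do not change the conclusion". Section 3.6 makes site the stratification factor: "Randomization will be stratified by clinical site".

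Section 5.2 and Appendix A size the trial on unadjusted proportions: 55% against 36.7%, 2.5% two-sided error per comparison, 90% power and 5% crossover, giving 630 women.

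**The concern.** Two things are wrong with the conditional sentence.

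First, it leaves the status of the adjusted result open. The adjustment is worded as something that will happen, and it is not labelled supportive. If an imbalance is found and the adjusted and unadjusted results fall on opposite sides of the 2.5% level, the plan does not say which one answers the primary question. The trigger could also be met for one comparison and not the other, so that the pessary and progesterone estimates come from different models.

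Second, the trigger selects on the wrong property. Under randomization, baseline differences are due to chance. Adjustment gains precision when the covariate predicts the outcome, whether or not the arms happen to differ on it. The protocol itself treats cervical length as prognostic: Section 2.2 reports preterm birth of 53.9% against 26.5% in twins with a shorter or longer cervix (cut-off 25 mm). Yet cervical length enters the model only if the arms happen to be unbalanced on it.

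At stake are a clearly defined confirmatory estimate for each arm and some power that could be had without extra patients.

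**Working it through.** **1. The plan's own figure.** Inputs from Section 5.2 and Appendix A: p1 = 0.55, p2 = 0.55 × 2/3 = 0.3667, two-sided error 0.025 (z = 2.241), power 90% (z = 1.282), mean rate p̄ = 0.4583.

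n = [2.241·√(2p̄(1−p̄)) + 1.282·√(p1(1−p1) + p2(1−p2))]² / (p1−p2)² = (2.241 × 0.7047 + 1.282 × 0.6926)² / 0.1833² ≈ 181.1, so 182 per group. Table 3 rounds this up to 190. The crossover factor is 1/0.95² = 1.108, so 190 × 1.108 = 210.5 per arm, or about 632 in total against 630 stated. The sample size reproduces.

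**2. Power of the unadjusted test after crossover (190 effective per arm).**
- One-third reduction: (0.1833·√190 − 2.241 × 0.7047)/0.6926 = 1.37, power 91%.
- 30% reduction (p2 = 0.385): (0.165·√190 − 2.241 × 0.7056)/0.6959 = 1.00, power 84%.

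Both meet the plan's statements of 90% and at least 80%.

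**3. What the rule does compared with planned adjustment.** The documents give neither the covariate's strength within the trial population nor a threshold. Assumed: one normally distributed baseline covariate with an odds ratio of 1.5, 2.0 or 2.5 per SD; imbalance declared at p < 0.05; adjustment by logistic regression; 190 per arm; one-sided 1.25%; 100,000 simulated trials per cell.

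Power at a 30% reduction:

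| Odds ratio per SD | Always unadjusted | Conditional rule | Always adjusted |
|---|---|---|---|
| 1.5 | 84.8% | 84.9% | 85.3% |
| 2.0 | 84.8% | 85.2% | 87.7% |
| 2.5 | 85.0% | 85.6% | 89.7% |

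Planned adjustment adds about 0.5 to 4.7 points over the unadjusted test, and the rule recovers about 0.1 to 0.6 of them. The simulated unadjusted power is slightly above the 84% from the normal approximation in step 2. Monte Carlo error is about 0.1 point.

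A separate simulation at the one-third reduction, with a combined covariate effect of 0.5 to 1.5 log-odds per SD and one or five factors, shows the same pattern: unadjusted about 92%, rule 92–93%, planned adjustment 93–98%.

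**4. Type I error (55% in both arms, nominal one-sided 1.25%).**

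| Procedure | Error over the three odds ratios |
|---|---|
| Always unadjusted | 1.3–1.4% |
| Always adjusted | 1.2–1.3% |
| Conditional rule, followed mechanically | 1.2–1.3% |
| Better of the two, only when the trigger fires | about 1.4% |
| Better of the two, in every trial | 1.5–1.8% |

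The rule itself holds its level. A clear excess needs a free choice between the two results in every trial.

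**5. How often the trigger fires.** With k independent factors tested at p < 0.05, the chance of at least one difference is 1 − 0.95^k: 5% for k = 1, 23% for k = 5, and 46% for k = 12 (the number of subgroup factors in Section 5.5). The documents fix neither k nor the threshold, so no single value can be given.

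**The case against.** The strongest reply is that a primary analysis is named, that it is unadjusted, and that the sample size is built on it. The center-adjusted analysis in the same paragraph is plainly supportive, and the conditional adjustment can be read the same way. That reading is reasonable, but the text does not state it, and the mandatory wording of the conditional sentence points the other way. The ambiguity therefore stands.

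Three stronger readings are tempting, and the documents do not support them.
- A reader might infer that the 2.5% error rate is lost. The trigger uses baseline data, not outcomes, and the rule applied as written holds its level. Nothing in Section 5.5 permits keeping the more favourable result.
- A reader might infer that the choice is made after unblinding. Section 5.5 gives no timing for the judgement; the gap is that no timing is given.
- A reader might infer that the switch will fire in nearly half of all comparisons. That needs about twelve independent known risk factors tested at p < 0.05. The list of twelve in Section 5.5 is for subgroups, not for adjustment.

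It can also be said that a fixed covariate set is only an efficiency preference, since declaring the unadjusted result confirmatory would settle the ambiguity. That is correct as far as the ambiguity goes. It would leave the available precision unused.

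**Conclusion.** The point holds as a gap in specification and a missed improvement. Section 5.5 does not say which result is confirmatory when its imbalance rule applies, and it uses chance imbalance where prognostic strength should decide.

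The cost is a forgone gain of about 0.4 to 4 percentage points of power at a 30% reduction (rule against planned adjustment). It is not a shortfall: the stated 90% and at least 80% are met without any adjustment. The size rests on an assumed odds ratio of 1.5–2.5 per SD. All enrolled women have a cervical length below 30 mm, and that restricted range may put the true value towards the low end or below it. The contrast in Section 2.2 includes women above that limit and does not settle the matter.

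The wording gap is certain; the size of the power gain is not. The change is worth making because it is cheap and removes discretion.

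**What to change.** In Section 5.5, delete the conditional sentence and state the following:
- One confirmatory model for each comparison, adjusting for site (the stratification factor), cervical length and gestational age at randomization, whatever the observed balance.
- The method for obtaining the adjusted relative risk and its confidence interval from that model, with the same statistic used at the interim looks in Section 5.4.
- The unadjusted comparison reported alongside.
- Any analysis prompted by an observed imbalance labelled as a sensitivity analysis that cannot replace the primary result.

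No new data or patients are needed, since all three covariates are already recorded at or before randomization. There is a small downside. The adjusted relative risk needs a model, and small sites may need pooling by a rule set in advance: Appendix A lists 18 centers, so a two-arm comparison of 420 women averages about 420/18 ≈ 23 per center.

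If the team prefers to keep the unadjusted analysis, one sentence is the minimum: the unadjusted result is confirmatory whatever the imbalance, and all adjusted results are supportive. That settles the ambiguity but gives up the gain in power.
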